9.3.2 Secondary Efficacy Variables

9.3.2.1 Operationalizations in Final Protocol

Secondary Efficacy Variables

- AUC for pain at rest in VAS from baseline to Day 4
- AUC for pain on passive movement in VAS from baseline to Day 2, 7 and Final Visit
- AUC for pain at rest in VAS from baseline to Day 2, 7 and Final Visit
- Change from baseline of pain on passive movement in VAS to Day 4, 7 and Final Visit
- Change from baseline of pain at rest in VAS to Day 4, 7 and Final Visit
- Change from baseline to Day 2, 4, 7 and Final Visit in the FAAM-ADL subscale
- Amount of rescue medication (doses)
- Time to 50% improvement of pain at rest measured by VAS at patient visits.

9.3.2.2 Additional Operationalizations

- AUC for pain on passive movement in VAS from baseline to Day 7 is defined as additional primary endpoint (see section 9.3.1.2), and, thus, removed from secondary efficacy variables.
- Descriptive procedures for secondary efficacy variables (1) to (7) will be performed according to section 9.1. Descriptive procedures for secondary efficacy variable 'time to 50% improvement' will be performed by means of frequency counts based on patient visits (50% improvement of pain at rest), as well as by Kaplan-Meier curves for time-to-event (including censored values). In addition to pain at rest (measured by VAS at patient visits), also pain on passive movement will be evaluated applying the same procedures.
- Test procedures for secondary efficacy variables (1) to (6) will be performed for the FAS and PP analysis sets as specified for the primary efficacy variable by analysis of covariance (see section 9.3.1.2), applying the associated baseline pain VAS as covariate. The test procedure for the secondary efficacy variable (7) will be performed for the FAS and PP analysis sets as specified for the primary efficacy variable by analysis of covariance (see section 9.3.1.2), applying baseline pain on passive movement in VAS as covariate. The secondary efficacy variable (8) will be analyzed by means of the Peto-Logrank test (time-to-event (logrank) test).
- Descriptive Procedures (Secondary Efficacy Variables (1) to (7)): TESTIMATE V6.5.14; PROC BASIC STATISTICS / SCIENCEGRAPH V4.9.39

- Descriptive Procedures (Secondary Efficacy Variable (8)): TESTIMATE V6.5.14;
 PROC KAPLAN-MEIER FUNCTION / SCIENCEGRAPH V4.9.39
- Test Procedures (Secondary Efficacy Variables (1) to (7): TESTIMATE V6.5.14;
 PROC ANALYSIS OF COVARIANCE
- Test Procedures (Secondary Efficacy Variable (8): TESTIMATE V6.5.14; PROC PETO-LOGRANK-TEST

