Hypothesis no. 1 (superiority) is based on the FAS analysis set, while hypothesis no. 2 (non-inferiority) is based on the PP analysis set. This way, both hypotheses are based on the more conservative data set.

If the first *a priori* ordered test (superiority) shows statistical significance, the subsequent hypothesis (non-inferiority) can then be tested individually in a confirmatory manner according to the principle of *a priori* ordered hypotheses (for control of alpha using stepwise testing see [Maurer et al. 1995]).

The confirmatory analyses will be performed using an analysis of covariance (ANCOVA) with baseline pain VAS as covariate. Due to the expected small number of patients per center, an additional inclusion of center as covariate will not be performed (see also EMA Guideline on adjustment for baseline covariates, section 4.2.3., EMA/295050/2013).

Exploratory Analyses

Details for analyzing the secondary efficacy parameters will be given in the SAP. Since all analyses of secondary efficacy parameters are exploratory in nature, no adjustment for multiplicity will be performed. Unless specified otherwise, treatment comparisons for the

secondary efficacy parameters are performed only for Traumed[®] gel versus placebo gel and Traumed[®] gel compared to diclofenac gel, respectively.

Sensitivity Analyses

Several pre-defined sensitivity analyses will be performed in order to demonstrate the robustness of the confirmatory results:

Data Sets

The two primary hypotheses (superiority, non-inferiority) will be evaluated additionally using the corresponding alternative data set (hypothesis no. 1: PP, hypothesis no. 2: FAS). The results of the sensitivity analyses will be compared with the confirmatory results.

Nonparametric Analysis

As a sensitivity analysis to the primary parametric approach, a nonparametric analysis will be performed for the two primary hypotheses.

The nonparametric procedures will be performed by means of the Wilcoxon-Mann-Whitney test. The Wilcoxon-Mann-Whitney test (WMW test) is the well-known robust test attributed to Wilcoxon (Wilcoxon 1945) and Mann and Whitney (Mann et al. 1947); for details of the test see e. g. Armitage, Berry, and Matthews (Armitage et al. 2002), or Sprent and Smeeton (Sprent et al. 2001).

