9.2.2 Additional Operationalizations

- Besides standard descriptive analyses (see section 9.1), formal homogeneity analyses for demographic variables and baseline characteristics will be performed based on the full analysis set (FAS) and the per-protocol set (PP). Robust Mann-Whitney estimators and their 95% confidence intervals will used as standardized summary measures across the relevant demographic-anamnestic variables (demography, physical examination, vital signs, supportive therapy, time and grading of injury) as well as across the efficacy criteria at baseline (VAS pain on passive movement, VAS pain at rest, FAAM). This will be performed in order to check baseline comparability of the three randomized groups in a robust, nonparametric way (minimized assumptions, independent from data type).
- As benchmark for relevant baseline differences, a Mann-Whitney estimator of 0.36 and 0.64 respectively will be applied (referring to a standardized difference of 0.5 according to Cohen, which is regarded as a medium-sized difference).
- In the case of inhomogeneities, stratified analyses will be performed by means of the Peto-Wilcoxon test (2 sided; 95% confidence interval, CI) with adjustment within the framework of the Cochran-Mantel-Haenszel pooling procedure (CMH pooling, also known as van Elteren pooling). For this purpose, depending on the respective data type and distribution, nominal categories, medians or quartiles of the affected baseline criteria will be used for stratification.

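### The ANCOVA covariate for the FAAM-ADL change score is given as an associated baseline pain VAS, which FAAM-ADL does not have; baseline FAAM-ADL should be named instead

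*SAP*

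**What the plan says.** SAP section 9.3.2.1 lists eight secondary efficacy variables. The sixth is "Change from baseline to Day 2, 4, 7 and Final Visit in the FAAM-ADL subscale". Section 9.3.2.2 then assigns the tests by number:

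- "Test procedures for secondary efficacy variables (1) to (6) will be performed for the FAS and PP analysis sets", by the ANCOVA of the primary variable, "applying the associated baseline pain VAS as covariate".
- Variable (7), the amount of rescue medication, uses the same ANCOVA, "applying baseline pain on passive movement in VAS as covariate".
- "The secondary efficacy variable (8) will be analyzed by means of the Peto-Logrank test".

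Section 9.2.2 of the SAP compares the groups on the "efficacy criteria at baseline (VAS pain on passive movement, VAS pain at rest, FAAM") and adds a stratified Wilcoxon-type analysis if a relevant imbalance is found. As the threshold, "a Mann-Whitney estimator of 0.36 and 0.64 respectively will be applied", which the SAP equates with a standardized difference of 0.5.

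Protocol section 11.1.3 leaves the details of the secondary analyses to the SAP and sets their status: "Since all analyses of secondary efficacy parameters are exploratory in nature, no adjustment for multiplicity will be performed".

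**The concern.** The covariate rule works only for outcomes that come from a pain VAS. FAAM-ADL is a 21-item function score on a 0 to 100 scale, so no baseline VAS belongs to it. Two baseline pain scores exist, at rest and on passive movement, and the rule does not choose between them for variable (6). Three readings are possible: VAS at rest, VAS on passive movement, or baseline FAAM-ADL on the view that the wording is a slip.

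The gap affects 4 visits x 2 treatment comparisons x 2 analysis sets = 16 tests. With a pain VAS as covariate, the analysis gives up the precision that the outcome's own baseline would provide, and the estimate moves with any chance imbalance in baseline FAAM-ADL. With no covariate named, the SAP also leaves a choice to be made later, possibly after unblinding.

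**Working it through.** **Which variable is (6).** In list order, (1) to (3) are AUCs of pain at rest or on passive movement, (4) and (5) are changes in those two scores, (6) is FAAM-ADL, (7) is rescue medication and (8) is time to 50% improvement. The logrank test for (8) and the separate rule for (7) confirm the numbering. Moving the Day 7 passive-movement AUC to the primary endpoints does not shift it, because item (2) keeps Day 2 and the Final Visit.

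**Whether other text fills the gap.** The reference back to the primary ANCOVA does not settle it. Variable (7) is analysed by the same reference, yet the SAP still names a specific VAS for it. The protocol defers to the SAP. The efficacy table, listing and figure lists in SAP section 13.3 do not mention FAAM at all; it appears only under baseline characteristics. Baseline FAAM-ADL is available: Protocol section 7.2.1 and Table 1 collect it on Day 1.

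**Size of the precision loss.** The plan states no figure to reproduce, and the documents give no FAAM-ADL standard deviation or correlations, so this is an illustration. Assumptions:

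- FAAM-ADL has the same standard deviation, scaled to 1, at baseline and follow-up.
- r is the correlation between baseline and follow-up FAAM-ADL, taken as 0.3 to 0.7.
- b is the correlation between baseline FAAM-ADL and baseline VAS, taken as 0 to -0.7.
- Baseline VAS is related to follow-up FAAM-ADL only through baseline FAAM-ADL.

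Residual variance of the change score:

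- adjusted for baseline VAS: 2(1 - r) - [b(1 - r)]²
- adjusted for baseline FAAM-ADL: 1 - r²

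| r | b | Own baseline | VAS | Ratio own/VAS |
|---|---|---|---|---|
| 0.3 | 0 | 0.910 | 1.400 | 0.65 |
| 0.3 | -0.7 | 0.910 | 1.160 | 0.78 |
| 0.5 | 0 | 0.750 | 1.000 | 0.75 |
| 0.5 | -0.7 | 0.750 | 0.878 | 0.85 |
| 0.7 | 0 | 0.510 | 0.600 | 0.85 |
| 0.7 | -0.7 | 0.510 | 0.556 | 0.92 |

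The square roots run from 0.81 to 0.96, so confidence intervals are about 4% to 19% narrower with the own baseline. Simulation with 312 and 156 patients gave variance ratios of 0.66, 0.80 and 0.91 at (r, b) = (0.3, 0), (0.3, -0.7) and (0.7, -0.7), and both estimators were unbiased.

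**Sensitivity to chance imbalance.** If the arms differ by 1 point in baseline FAAM-ADL, the VAS-adjusted estimate shifts by (1 - r) = 0.3 to 0.7 points when baseline VAS is balanced. Averaged over the VAS imbalance that would accompany it, the shift is (1 - r)(1 - b²): from 0.3 x 0.51 = 0.15 up to 0.7 x 1 = 0.70 points.

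**Whether the baseline check in section 9.2.2 would catch it.** Removing the 184 issue patients from the planned 808 leaves 624, or about 312 and 156 for Traumed and placebo if they fell in the 2:1:1 ratio (the visible text does not give the split by arm).

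- Standard error of the standardized difference: √(1/312 + 1/156) = 0.098.
- Threshold: 0.5/0.098 = 5.1 standard errors, two-sided probability 3.4 x 10⁻⁷. The equivalence to the Mann-Whitney value checks: Φ(0.5/√2) = 0.638.
- An imbalance of 1.96 standard errors is only 1.96 x 0.098 = 0.19 standard deviations, so ordinary chance imbalances would almost never trigger the stratified analysis.

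**The case against.** The strongest reply is that this is a clerical slip. A phrase written for (1) to (5) was stretched to (6), each variable's own baseline was intended, and on that reading nothing is lost. That may be so, but the SAP does not say it. The precision figures apply only if a pain VAS is in fact used.

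Second, other controls limit a free choice after unblinding. Sections 9.1 and 13.4.1 fix metadata, the report template and a mock report before the blind is broken, and section 11 requires major later changes to be reported with a rationale. These make a silent choice less likely. They do not name the covariate.

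Third, section 9.2.2 reports the Mann-Whitney estimate and confidence interval for baseline FAAM whether or not the threshold is reached, so an imbalance would be visible. That is correct, but seeing an imbalance does not adjust for it.

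Fourth, the illustration takes its correlations and equal standard deviations from assumption, and the true values could lie outside the ranges in either direction. That stands.

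Fifth, the endpoint is exploratory, either covariate gives an unbiased comparison on average, and chance imbalance is already part of the reported standard error, so it is not a separate bias. That also stands and limits the weight of the point.

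**Conclusion.** The concern holds. The rule assigns FAAM-ADL a covariate that does not exist for it, does not say which pain score would stand in, and leaves out the matching baseline that the trial collects.

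The effect is modest. The confirmatory sequence does not use FAAM-ADL, and a pain-VAS covariate would not invalidate the comparison; the change score already subtracts baseline. Subtraction does not remove the dependence on baseline, however. In the earlier ankle-sprain trial described in Protocol section 3, baseline FAAM-ADL ranged from 2.4 to 98.3 on a scale that ends at 100, so the possible gain ranged from 97.6 points down to 1.7.

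If a pain VAS is used, the cost is a confidence interval that baseline FAAM-ADL would make about 4% to 19% narrower, and a shift of roughly 0.15 to 0.7 points per point of baseline imbalance. Both ranges rest on the assumed correlations, equal standard deviations and dependence structure. That the covariate is missing rests on the text alone and needs no assumption.

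**What to change.** In SAP section 9.3.2.2, split the rule before unblinding: variables (1) to (5) use the baseline value of the pain VAS from which the outcome is derived, and variable (6) uses the baseline FAAM-ADL score. The rest of the ANCOVA specification can stay as it is.

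The cost is one phrase. The data are already collected on Day 1, and no confirmatory analysis changes. If the SAP has already been signed and the blind broken, state the covariate used and the reason for it in the trial report under the provision of SAP section 11.

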11.1.3. Analysis of Efficacy Parameters

The summaries of the efficacy parameters, the statistical analyses of the primary efficacy variable, and the statistical analyses of the secondary efficacy variables will be performed on the Full Analysis Set (primary set for evaluation of superiority of Traumed[®] gel versus placebo, secondary set for evaluation of non-inferiority of Traumed[®] gel compared to diclofenac gel), and on the PP set (primary set for evaluation of non-inferiority of Traumed[®] gel compared to diclofenac gel, secondary set for evaluation of superiority of Traumed[®] gel versus placebo).

Missing values for all efficacy parameters will be imputed by the last observation carried forward (LOCF) approach. In addition, a last percentile carried forward approach (LPCF) will be performed as sensitivity analysis (see also section 11.1.4). Further sensitivity analyses resulting from the blind review of the data will be provided in the final SAP.

All statistical tests will be two-sided with a significance level of $\alpha=0.05$, unless specified otherwise. Where appropriate, statistical tests will be supported by presenting estimates and 95% confidence intervals for the respective treatment effects and differences between the treatment groups. These estimates and confidence intervals will be based on the respective statistical models used for the analysis.

In the study of Schomacher (Schomacher 2008), the clinically relevant difference between VAS scores showed varying results. In the case of low baseline VAS scores the clinically relevant reduction in VAS values starts at 5 to 10 of 100 mm whereas with higher baseline VAS scores minimal change of 20 mm or 30% may be indicated. Nevertheless, the review of Schomacher was not limited to pain of joints of extremities.

In the study of Tubach et al. (Tubach et al. 2005 a/b) the MCII (minimal clinically important improvement) of pain for knee and hip osteoarthritis was evaluated. The absolute (and relative) changes were, respectively, (a) -19.9 mm (-40.8%) and -15.3 mm (-32.0%) for pain.

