The time to 50 % improvement will be calculated from VAS assessments on pain at rest performed at all patient visits using the percent changes from baseline (recorded at Day 1).

Rescue medication

The rescue medication use will be documented in the eCRF based on the information given in the patient diary and the drug accountability for rescue medication during the study.

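### Time to 50% improvement is the one secondary variable whose planned test has no baseline pain term; stratifying its logrank test may recover some power at almost no cost.

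*SAP*

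**What the plan says.** SAP 9.3.2.2 assigns the tests for the eight secondary variables listed in SAP 9.3.2.1.

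- Variables (1) to (6), the AUCs, the changes in VAS and the change in FAAM-ADL, are tested "by analysis of covariance (see section 9.3.1.2), applying the associated baseline pain VAS as covariate".
- Variable (7), amount of rescue medication, also gets an analysis of covariance, "applying baseline pain on passive movement in VAS as covariate".
- For variable (8), time to 50% improvement, "The secondary efficacy variable (8) will be analyzed by means of the Peto-Logrank test (time-to-event (logrank) test"). The procedure named is PROC PETO-LOGRANK-TEST, with no covariate and no strata. The same section adds an analysis of pain on passive movement by the same procedures.

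SAP 6.3.2 derives the event from rest-pain VAS assessments "performed at all patient visits using the percent changes from baseline (recorded at Day 1"), so improvement can be seen only at a visit.

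One other SAP provision concerns baseline differences. SAP 9.2.2 states: "In the case of inhomogeneities, stratified analyses will be performed by means of the Peto-Wilcoxon test". There, "medians or quartiles of the affected baseline criteria will be used for stratification".

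Protocol 11.1.3 calls all secondary analyses exploratory and makes no multiplicity adjustment.

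**The concern.** Seven of the eight secondary variables are tested with a baseline pain term and the eighth is not, with no reason given. If baseline rest pain predicts how soon a patient reaches a 50% reduction, an unstratified logrank test leaves that variation in the comparison and has less power than a test that accounts for it. The matching baseline VAS is recorded on Day 1 for both kinds of pain, so the information is available at no cost.

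SAP 9.2.2 does not fill the gap. It is triggered only by baseline imbalance between groups, whereas the power question arises even when the groups are perfectly balanced. It also specifies the Peto-Wilcoxon test rather than the logrank test.

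At stake is the sensitivity of one exploratory comparison (Traumed gel against placebo, and likewise against diclofenac gel). No confirmatory hypothesis depends on it.

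**Working it through.** **The plan's own figure.** The documents give no power, hazard ratio or event count for variable (8). Their only power statement for a treatment comparison is for the primary AUC (Protocol 11.4): difference 25, SD 75, two-sided 0.05, at least 90% power, 291 against 146 patients. With 2:1 allocation the placebo group needs (1 + 1/2) × (1.960 + 1.282)² × (75/25)² = 1.5 × 10.51 × 9 ≈ 142, and Traumed 284. At 291 and 146 the standard error is 75 × √(1/291 + 1/146) = 7.61, so power is Φ(25/7.61 − 1.96) = 90.8%. The figure reproduces but says nothing about variable (8).

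**Does a percent-of-baseline event still depend on baseline?** Let B be baseline pain.

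- If pain at time t is B × f(t), with f unrelated to B, the event occurs when f(t) ≤ 0.5. B drops out.
- If pain falls by an amount D(t) unrelated to B, the event occurs when D(t) ≥ B/2. Low-baseline patients get there sooner.

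Illustrative models, none with inputs from the documents, confirm that both cases are possible.

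- With proportional decline at rates unrelated to baseline (mean 40 mm, SD 12 to 18 mm, VAS noise 0 to 8 mm), the log hazard ratio per SD of baseline was −0.03 to 0.05.
- In a second model (mean 35 mm, SD 18 mm), the share reaching 50% by Day 4 in the lowest against the highest baseline quartile was 31% vs 31% for proportional decline without noise and 48% vs 36% with 5 mm noise. With 10 mm noise it was 50% vs 50% at Day 4, but 25% vs 13% at Day 2. For additive decline it ranged from 88% vs 3% to 68% vs 30%.

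The dependence may therefore be absent or strong, and the documents do not say which.

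**Power.** Events were generated with proportional hazards and observed only at the visits 1, 3, 6 and 13 days after baseline (Days 2, 4, 7 and 14). The test statistic is Z = Σ(O − E)/√ΣV. At each visit E = d·n₁/n and V = d·(n₁/n)(1 − n₁/n)(n − d)/(n − 1), where d is the number of events, n the number at risk and n₁ the number at risk on Traumed. The sums run over visits and, for the stratified test, also over baseline quartiles.

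Setting A: 291 vs 146 patients (the primary sample size), assumed hazard ratio 1.35, and about 12/39/66/86% of placebo patients improved by the four visits. It was run twice independently; both results are shown.

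| Log hazard ratio per SD | Unstratified | Stratified | Gain (points) |
|---|---|---|---|
| 0 | 77%; 78% | 77%; 78% | 0; 0 |
| 0.25 | 74%; 74% | 76%; 76% | 2; 2 |
| 0.5 | 65%; 66% | 73%; 74% | 8; 8 |
| 0.75 | 56%; 54% | 71%; 72% | 15; 18 |

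Setting B: 312 vs 156 patients, assumed hazard ratio 1.4, and exponential times with 0.13 per day on placebo. The sample size is 808 − 184 issue patients = 624, split 2:1:1 on the assumption that the exclusions fall in proportion.

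| Log hazard ratio per SD | Unstratified | Stratified | Gain (points) |
|---|---|---|---|
| 0 | 86.8% | 86.6% | −0.2 |
| 0.2 | 85.8% | 86.9% | 1.1 |
| 0.4 | 80.7% | 85.0% | 4.3 |
| 0.7 | 68.6% | 82.1% | 13.5 |

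**Type I error.** With a hazard ratio of 1, both tests stay near 5%. In setting B at 0.4 per SD, each gave 5.1% in 10,000 runs.

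**The case against.** The strongest reply is that nothing here is an error. The logrank test holds its level, an unadjusted logrank test with Kaplan-Meier curves is a legitimate choice, and variable (8) is exploratory with no stated power. The event is already scaled to baseline, so zero dependence is a natural case, and there the loss is nil. The hazard ratio, event rates and prognostic strength are all assumed. Unadjusted rank tests also appear elsewhere in this SAP: the Wilcoxon-Mann-Whitney and Wei-Lachin analyses in 9.4.1.2 name no baseline covariate. For the added passive-movement analysis, entry requires VAS above 50 mm, so the baseline range is truncated, and the simulations address rest pain only. All of this stands. It limits the size and status of the point but does not explain why variable (8) differs from (1) to (7), and it does not make stratification costly.

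A reader might also infer stronger claims that the documents do not support.

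- *That Protocol 11.1.3 shows baseline to be prognostic, because* "In the case of low baseline VAS scores the clinically relevant reduction in VAS values starts at 5 to 10 of 100 mm". That sentence concerns how large a change is clinically relevant, not who recovers sooner. Its second half gives larger values for higher baselines, which if anything supports a percent definition.
- *That the treatment ratio is pulled toward 1.* The SAP plans no hazard ratio for variable (8). Marginal and conditional ratios also differ by definition, which is not bias.
- *That variable (8) becomes non-comparable with (1) to (7).* A logrank statistic and an ANCOVA mean difference are on different scales with or without strata.
- *That this is the only measure of speed of relief.* The AUCs to Day 2 and Day 4 also reflect early relief.

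For FAAM-ADL, variable (6), "applying the associated baseline pain VAS as covariate" is ambiguous because FAAM is not a pain VAS. A baseline pain covariate is nevertheless named.

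**Conclusion.** The point holds as a possible, avoidable loss of efficiency on an exploratory endpoint. By the text of SAP 9.3.2.2, variable (8) alone lacks a baseline pain term, and SAP 9.2.2 does not supply one. The planned test is valid, and no confirmatory conclusion is affected.

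The loss cannot be derived from the documents. Under assumed hazard ratios of 1.35 to 1.4 it is:

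- nil if baseline is not prognostic;
- about 1 to 2 points of power at a log hazard ratio of 0.2 to 0.25 per SD;
- about 4 to 8 points at 0.4 to 0.5;
- about 14 to 18 points at 0.7 to 0.75.

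The trade favours stratifying: it costs under 1 point when baseline does not matter and gains power when it does. This is a free improvement, not the correction of a mistake.

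**What to change.** Before unblinding, amend SAP 9.3.2.2 so that the logrank test for variable (8) is stratified by quartile of the matching baseline VAS: rest pain for the rest-pain analysis, passive-movement pain for the additional one. Take the quartile cut points from all treatment groups pooled, so that they can be fixed blind. Keep the unstratified logrank test and the Kaplan-Meier curves as supportive description.

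The cost is one sentence in the SAP and one further test run after unblinding, with no new data. SAP section 3 places sign-off after hard lock and before unblinding, so the amendment fits that window. The documents do not say whether PROC PETO-LOGRANK-TEST accepts strata; the trial statistician should confirm this when making the change.
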